Multicenter Clinical Observation Using the Cementless Version of the POLARSTEM®

SUMMARY	2
1 STUDY OBJECTIVES	3
1.1 Background	3
1.2 The POLARSTEM®.....	3
1.3 Objectives	4
2 STUDY DESIGN	5
2.1 Patient selection	5
2.2 Sample size consideration.....	6
2.3 Study duration	6
2.4 Pseudonymisation of patient identifiable information.....	6
3 STUDY METHOD	7
3.1 General	7
3.2 Postoperative rehabilitation	7
3.3 Follow-up.....	7
3.4 Complications/adverse events/lost-to follow-up.....	8
3.5 Patient recruitment	8
4 DESCRIPTION OF THE DEVICES	9
4.1 Implants	9
4.2 Instruments	9
5 ETHICAL AND LEGAL ASPECTS	10
5.1 Ethical aspects	10
5.2 Legal aspects.....	10
6 PARTNERS	11
6.1 Study sponsor and monitor	11
6.2 Investigators	11
6.3 Publication policy	12
7 SIGNATURE	13
8 REFERENCES	14

SUMMARY

Objective: Validation of the POLARSTEM® as state-of-the-art implant in terms of radiographic, clinical performance and long-time survivorship.

Study design: Prospective study

Study population: Total of 225 patients in 3 different sites

Intervention (if applicable): Implantation of a total hip prosthesis

Main study parameters/endpoints: Radiographic: radiolucent lines, osteolysis, hypo- or hypertrophy; implant loosening or migration; Clinical: Harris Hip Score and HOOS Score

Nature and extent of the burden and risks associated with participation, benefit and group relatedness: Patients will benefit without restriction from their total hip prosthesis. Patients enrolled in this study will receive the same operation and the same follow-up treatments as patients not enrolled. Therefore, no additional risks are expected.

1 STUDY OBJECTIVES

1.1 Background

Total hip arthroplasty (THA) has been an established treatment procedure for patients suffering osteoarthritis of the hip and other joint diseases. However, THA alters the distribution of mechanical forces around the hip joint leading to bone remodeling related to implant design and mechanical properties as implied by Wolff's law. According to this law, an implantation of a femoral prosthesis induces a reduction of the proximal compressive stresses and a reactive loss of the proximal femoral bone mass. Although stress shielding has been described as clinically irrelevant with some stem designs (i.e., double-tapered form) [1], others suggest that this phenomena can compromise the implant stability and thus the clinical outcome of a THA and may predispose to loosening, migration as well as complications of the implant during revision [2, 3]. Furthermore, proximal radiolucent lines may provide wear particles (e.g., polyethylene) the possibility to migrate along the bone-implant interface, enlarging the risk of osteolytic processes [4].

Hydroxyapatite (HA) coatings have been widely used in THA due to their osseointegrative properties [5, 6]. HA on proximal stems have been shown to improve osseointegration, thus facilitating load transmission in the metaphysal part of the femur and hence reduced stress shielding. An improved osseointegration may also function as a barrier to migration of wear debris to the bone-implant interface, eventually leading to reduced osteolysis and increased implant long-term survival.

1.2 The POLARSTEM®

The POLARSTEM® is a double-tapered stem with a large proximal part and a short and slim distal end and it is forged from a Ti-6Al-4V alloy. The neck of the POLARSTEM® is mirror-polished to reduce the risk of insert damage during impingement. The bone-contacting part of the stem is coated with a ground layer from porous titanium (150 µm) and covered with a HA-coating (80 µm) offering excellent primary stability and improved osseointegration. Furthermore, the POLARSTEM® exhibits proximal grooves perpendicular to the internal curve and to the average load direction to reduce the risk of implant subsidence. For increased rotational stability the stem also features distal grooves reversed to the rotational direction.

Fig. 1: Cementless version of the POLARSTEM® made from a Ti-6Al-4V alloy exhibiting its characteristic grooves on the hydroxyapatite (HA)-coating (see text for details).

1.3 Objectives

The goal of this multicenter clinical observation is to validate short-, mid-, and long-term outcome (efficacy and safety) of the POLARSTEM®.

Efficacy evaluations

- Evaluation of function, range of motion (ROM) and pain as assessed by Harris Hip Score, Hip disability and osteoarthritis outcome score (HOOS) [7, 8], an extension of the Western Ontario and McMaster Universities Osteoarthritis Index (WOMAC).
- Radiographic changes as defined by radiolucent lines, osteolysis, hypo- and hypertrophy, implant loosening or migration

Safety evaluations

- Intra- and perioperative device-related adverse events (AE) and complications up to discharge
- Postoperative AE up to 10 years

Long-term survivorship will be calculated according to Kaplan-Meier with stem revision due to any reason as endpoint.

2 STUDY DESIGN

This is a prospective long-term multicenter clinical observation study using the cementless version of the POLARSTEM®. Overall, a minimum of 225 patients will be enrolled in 3 sites. Each site will enroll the patients consecutively; the number of patients per site will be defined together with each investigator.

2.1 Patient selection

Patients enrolled in this multicenter clinical observation will have at least one of the indications listed below and meet all of the inclusion criteria. Patients meeting any of the exclusion criteria are not eligible for this study.

Indications

- Primary or secondary coxarthrosis
- Rheumatoid arthritis
- Developmental dysplasia of the hip (Crowe type I and II)
- Fracture or avascular necrosis of the femoral head

Inclusion criteria

- Patient has no general medical contraindication to surgery
- Informed consent to participate in the MCO signed by the patient
- Routine radiographic assessment is possible
- Patient is likely to comply with study follow-up requirements
- Primary total hip replacement (THR) to the affected side, unilateral or bilateral

Exclusion criteria

- Previously failed endoprosthesis and /or THR components in relevant hip
- History of infection in the affected joint; systemic infections
- Grossly insufficient femoral or acetabular bone stock in the involved hip
- Charcot joint disease or other severe neurosensory deficit
- Severe spinal disorders
- Age of patient at date of surgery > 75 years

- High comorbidity
- Cemented acetabular cup

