2.2 Sample size consideration

Sample size estimations have been made on the assumption that for a valid statistical data analysis according to Kaplan-Meier, at least 100 implants surviving 10 years are necessary. Over a period of 10 years, a drop-out rate of 30% should be considered. Therefore, 150 initial implantations are needed in each group.

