7.2 Analysis Populations

All subjects who provide informed consent are considered study participants. Study populations are defined as follows:

CONFIDENTIAL AND PROPRIETARY

This document contains information that is confidential and proprietary to Smith & Nephew PLC and Smith & Nephew, Inc. and is intended for use only by Smith+Nephew and its manufacturer. It shall not be reproduced or copied in whole or in part, nor shall the contents be disclosed by any means without prior written permission from Smith+Nephew, nor shall anyone make any use of it that is contrary to the expressed or implied wishes of Smith+Nephew.

Statistical Analysis Plan

Multicenter Clinical Observation Using the Cementless Version of the POLARSTEM™

Number: D10070
ST: 1133
Version: 1.0, 30-Nov-2021
Page: 9 of 19

- **Full analysis population (FAS)**, including all subjects that were included in the study, who received study treatment and attended at least one post baseline assessment.
- **Per protocol analysis population**, including all subjects in the full analysis population, have no significant protocol deviations and meet the inclusion/exclusion criteria.
- **Safety population**, including all subjects who have received study treatment.

Statistical analysis will be performed using each of the subject populations as follows: Analysis of primary, secondary and exploratory variables will be performed separately using both the FAS and the Per-Protocol Set. All safety analyses will utilise the Safety Population. Demographic characteristics will be summarized for each analysis population. Demographic characteristics will be summarized on a subject level. For bilateral subjects the data corresponding to the date of the hip's first enrolment into the study will be used.

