7.10 Analysis of Primary Endpoint

- Short term, medium term and long term survival rates.
- Survival rates will be presented with a 95% confidence intervals at 3 months and at 1 year, 3 year, 5 year and 10 year postoperative time points from Kaplan-Meier product limit estimates.
- The revisions (by type of revision) will be tabulated and/or listed.

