7.11 Analysis of Secondary Endpoints

- Harris Hip Score (HHS)

CONFIDENTIAL AND PROPRIETARY

This document contains information that is confidential and proprietary to Smith & Nephew PLC and Smith & Nephew, Inc. and is intended for use only by Smith+Nephew and its manufacturer. It shall not be reproduced or copied in whole or in part, nor shall the contents be disclosed by any means without prior written permission from Smith+Nephew, nor shall anyone make any use of it that is contrary to the expressed or implied wishes of Smith+Nephew.

Statistical Analysis Plan

Multicenter Clinical Observation Using the Cementless Version of the POLARSTEM™

Number: D10070
ST: 1133
Version: 1.0, 30-Nov-2021
Page: 17 of 19

- HOOS Score (Hip Dysfunction and Osteoarthritis Outcome Score), which includes the complete WOMAC Osteoarthritis Index
 - The different dimensions of and the overall HHS, and WOMAC from HOOS scores at all recorded time points and end of study will be summarized using mean, median, SD, minimum, and maximum. A paired sample t-test (or a non-parametric equivalent such as the Wilcoxon signed-rank test) will be used to test the difference between preoperative and postoperative scores.
- Radiological: At all recorded time points (from the perioperative through the 10 year postoperative follow-up), the following analyses would be carried out:
 - For general findings: At the acetabulum position, cranial migration (mm), medial migration (mm) and tilted angle would be summarized using descriptive characteristics for continuous variables; At the stem position, varus tilting, valgus tilting and sunken (mm) will be summarized using descriptive statistics for continuous variables; Integration in general/acetabulum, integration in general/stem and ectopic ossification will be summarized using descriptive statistics for categorical variables.
 - Within the cup and the stem (by zone): The number and percent of hips with osteolysis will be summarized; for seams (0mm, 1mm, 2mm &>2mm), atrophy (none, mild, moderate & severe) and hypertrophy (none, mild, moderate & severe) their frequencies (n) and percentages will be presented.

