7.15 Changes in Analysis Methods Specified in the Protocol

There is a discrepancy in the protocol in regards to the sample size requirements for this study. In the “Study Design” section of the protocol, it is stated that a minimum of 225 subjects will be enrolled in 3 sites whereas in the “Sample Size Consideration” of the protocol, it is stated that “Sample size estimations have been made on the assumption that for a valid statistical data analysis according to Kaplan-Meier, at least 100 implants surviving 10 years are necessary. Over a period of 10 years, a drop-out rate of 30% should be considered. Therefore, 150 initial implantations are needed in each group”.

A total of 225 subjects was eventually enrolled and implanted with the study device.

CONFIDENTIAL AND PROPRIETARY

This document contains information that is confidential and proprietary to Smith & Nephew PLC and Smith & Nephew, Inc. and is intended for use only by Smith+Nephew and its manufacturer. It shall not be reproduced or copied in whole or in part, nor shall the contents be disclosed by any means without prior written permission from Smith+Nephew, nor shall anyone make any use of it that is contrary to the expressed or implied wishes of Smith+Nephew.

Smith+Nephew

Statistical Analysis Plan

Multicenter Clinical Observation Using the Cementless Version of the
POLARSTEM™

Number: D10070
ST: 1133
Version: 1.0, 30-Nov-2021
Page: 19 of 19

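### Bilateral patients are eligible, but the SAP neither names the stem as unit nor allows for two hips in one patient, so per-hip intervals would be somewhat too narrow

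*Protocol*

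**What the plan says.** **Eligibility.** Protocol 2.1 lists among the inclusion criteria "Primary total hip replacement (THR) to the affected side, unilateral or bilateral". The SAP expects such patients: 7.5 records the operated hip with bilateral as a category, 7.6 reports disposition by subject and by hip, and 7.2 has a rule for bilateral subjects.

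**The unit varies by section.**
- *Implants or stems.* Protocol 1.3 makes revision of the stem, whatever the cause, the survival event. Protocol 2.2 sizes the study for Kaplan-Meier on the basis that "at least 100 implants surviving 10 years are necessary".
- *Patients.* Protocol 2 counts enrolment in patients: "Overall, a minimum of 225 patients will be enrolled in 3 sites". SAP 7.15 reports: "A total of 225 subjects was eventually enrolled and implanted with the study device". It gives no hip count. SAP 7.2 defines the analysis populations by subject, and SAP 7.3 speaks of censoring subjects.
- *Hips.* In SAP 7.11, for cup and stem zones: "The number and percent of hips with osteolysis will be summarized".
- *Not named.* The primary endpoint (SAP 5.1), the survival time and revision indicator (SAP 7.4), the Kaplan-Meier analysis (SAP 7.10: "Survival rates will be presented with a 95% confidence intervals") and the paired score tests (SAP 7.11).

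**The one bilateral rule.** SAP 7.2 says: "For bilateral subjects the data corresponding to the date of the hip's first enrolment into the study will be used". It comes directly after the sentence that puts demographic summaries at subject level.

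Neither document mentions clustered variance, a frailty term, a patient effect or a one-hip-per-patient rule for survival or scores.

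**The concern.** Two hips in one patient share bone quality, activity level, comorbidity and often the surgeon, so their outcomes may be positively correlated. The usual Kaplan-Meier variance and the paired t-test or signed-rank test assume independent records. If each hip enters as its own record, the survival estimate itself is not distorted by this, but its standard error is too small.

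For the scores, part of the dependence is built in. Walking distance, support, stairs and public transport in the HHS, and shopping and domestic tasks in the WOMAC, describe the person rather than one hip.

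What is at stake is the stated precision of the primary output, a survival rate with a 95% interval. The analysis also cannot be programmed without an unrecorded choice: SAP 7.4 starts survival time at the baseline assessment and does not say which preoperative visit starts the clock for a second hip operated on later.

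**Working it through.** **1. The plan's own figure.** Protocol 2.2 needs 100 surviving implants and adds: "Over a period of 10 years, a drop-out rate of 30% should be considered". Then 100/(1 − 0.30) = 142.9, so 143 implants. The protocol states 150 per group; 150 × 0.70 = 105, which meets the target of 100. The stated figure is therefore 143 with some margin. It is counted in implants, and the present point does not depend on it.

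**2. Inputs.** Number of patients: 225 (SAP 7.15). Share of patients with both hips enrolled, *b*: not given, assumed. Correlation between the two hips of a patient, ρ: not given, assumed.

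**3. Formulas.**
- Hips = 225(1 + *b*)
- Share of hips that belong to a pair = 2*b*/(1 + *b*)
- Design effect DE = 1 + ρ · 2*b*/(1 + *b*)
- Factor by which the per-hip interval must be widened = √DE
- Real coverage of a nominal 95% interval = P(|Z| < 1.96/√DE)

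Example with *b* = 20% and ρ = 0.5: 2 × 0.2/1.2 = 0.333; DE = 1 + 0.5 × 0.333 = 1.167; √DE = 1.080; 1.96/1.080 = 1.815, which gives coverage of 93.0%.

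**4. Results for ρ = 0.1 and ρ = 0.5.**

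| *b* | Hips | DE | Widening factor | Real coverage |
|---|---|---|---|---|
| 2% | 229.5 | 1.004 to 1.020 | 1.002 to 1.010 | 94.96% to 94.77% |
| 5% | 236.2 | 1.010 to 1.048 | 1.005 to 1.024 | 94.89% to 94.45% |
| 10% | 247.5 | 1.018 to 1.091 | 1.009 to 1.044 | 94.79% to 93.94% |
| 20% | 270.0 | 1.033 to 1.167 | 1.017 to 1.080 | 94.62% to 93.04% |

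The bound at *b* = 20% and ρ = 1 is a factor of 1.155 and coverage of 91.0%.

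**5. On the survival scale.** Assume 97% ten-year survival and constant hazards of revision and of drop-out, with 30% drop-out by ten years. With Greenwood's variance:
- *b* = 10%: the half-width per hip is 2.33 percentage points if pairs are ignored, and 2.35 to 2.43 if they are allowed for.
- *b* = 20%: 2.23 points, against 2.27 to 2.41.
- First hip only (225 hips): 2.44 points, with no pairing left to correct.

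**6. What the correlation means for a rare event.** With revision risk *q*, the risk for the second stem given revision of the first is *q* + ρ(1 − *q*). At an assumed *q* = 3%, ρ = 0.1 gives 0.03 + 0.097 = 12.7%, and ρ = 0.5 gives 0.03 + 0.485 = 51.5%. For revision, the lower end of the range is therefore the easier one to defend.

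**The case against.** **The survival unit is not wholly open.** The protocol makes stem revision the event and sizes Kaplan-Meier in implants. SAP 7.15, which lists departures from the protocol, repeats the implant-based reasoning and announces no move to patients. This stands: the implant is the natural reading and the SAP merely fails to restate it. But that is exactly the reading under which pairing is ignored.

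**A reader might infer that second stems drop out of the primary endpoint.** That would follow if the first-hip rule in SAP 7.2 governed every analysis: about 22.5 of 247.5 stems (9.1%) at 10% bilateral, or 45 of 270 (16.7%) at 20%. The documents do not favour this. The rule directly follows the sentence on demographics and reads most naturally as part of it.

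**A reader might also infer that every reading gives either a wrong interval or an incomplete endpoint.** That is too strong. Time to first revision of either stem, one record per patient, counts revisions on both sides and has a valid interval, though it estimates something other than stem survival. A first-hip analysis also has a valid interval.

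**The scores may already be one record per patient.** The HHS table in SAP 7.4 writes the total as a sum for each subject, and patients complete the HOOS themselves (Protocol 3.1). This has weight, but SAP 7.11 does not say so.

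**No decision turns on it.** The study has one arm, with no survival hypothesis, performance goal or margin in the documents, and the radiographic results are descriptive. This stands and limits the severity.

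**Conclusion.** The point holds, as a minor one. The stated methods make no allowance for paired hips, and per-hip analysis then gives intervals that are too narrow whenever some patients have both hips enrolled and their outcomes are positively correlated. The direction is clear under those two conditions; the size is not known.

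At 10-20% bilateral and ρ of 0.1-0.5, all assumed, the widening needed is about 1-8% and real coverage is about 94.8% to 93.0%. In the 97% survival illustration this is 0.02 to 0.18 percentage points of half-width. At 2% bilateral it is negligible.

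A much larger loss can be produced: 30% bilateral with ρ = 0.7 gives DE = 1 + 0.7 × 0.6/1.3 = 1.323 and coverage of 91.2%. Nothing in the documents supports either value, and for a 3% event that ρ would mean a 71% revision risk for the second stem once the first is revised.

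**What to change.** In SAP 7.10 and 7.11, with the matching definitions in 7.4:

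- State that the stem (hip) is the unit for survival and that each hip has its own start date.
- Report the number of hips and the number of bilateral patients, so that readers can judge whether pairing matters.
- Give Kaplan-Meier confidence intervals with patient-clustered (robust) variance, or from a bootstrap that resamples patients.
- For HHS and WOMAC, either use one hip per patient by a stated rule, or use a method that accounts for patient, such as a mixed model with a patient random effect.
- Add a first-hip-only sensitivity analysis for survival. If revisions are few, the clustered variance is itself imprecise, and this analysis is a simple check on it.
- State in SAP 7.2 that the first-hip rule covers demographics only, if that is the intention.

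The cost is a few sentences, a little programming and slightly wider intervals. The SAP already plans disposition by hip and records bilateral operations, so no new data collection should be needed.

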2.2 Sample size consideration

Sample size estimations have been made on the assumption that for a valid statistical data analysis according to Kaplan-Meier, at least 100 implants surviving 10 years are necessary. Over a period of 10 years, a drop-out rate of 30% should be considered. Therefore, 150 initial implantations are needed in each group.

2.3 Study duration

It is expected to enroll all patients within 12 months. Each patient will be called for follow-up investigations after 3 months, 1 year, 3 years, 5 years, and 10 years.

2.4 Pseudonymisation of patient identifiable information

Patients' data are pseudonymized using a consecutive number according to their study enrolment.

3 STUDY METHOD

3.1 General

Patients' pre-operative status, surgical procedure as well as clinical and radiological outcome will be documented by means of Case Report Forms (CRFs) that are provided by the study sponsor. CRFs will be filled in the investigator or specially assigned hospital personnel who have been trained for the study. Completed CRFs are faxed from the site to the sponsor immediately upon completion. Case Report Forms are the basis for further data evaluation.

Pain, function, gait, range of motion (HHS) and radiographic status determinations are made pre-operatively and at each post-operative examination. Radiographic analysis will be done on standard AP and lateral view X-rays.

Pre-and postoperative HOOS questionnaires are filled in by the patients themselves. Patients must have the possibility to complete the forms on their own, without any external influence. This means patients should have the possibility to take the questionnaire home and return it to the hospital at a later date.

3.2 Postoperative rehabilitation

Postoperative rehabilitation is carried out according to each hospital's standard procedure.

3.3 Follow-up

The follow-up schedule is shown in table 1.

Table 1: Time windows for investigations

	Time-window	HHS/HOOS	Clinical	Radiographic
Preoperative	45–0 days	X	X	-
3 months	10–14 weeks	X	X	X
1 year	11–13 months	X	X	X
3 years	36–38 months	X	X	X
5 years	60–63 months	X	X	X
10 years	120–123 months	X	X	X

3.4 Complications/adverse events/lost-to follow-up

Complications and adverse events are noted at each follow-up interval. For completed observations due to death of the patient, explantation of the device or patient's address unknown the latest status will be recorded as an endpoint. Patients will be considered lost to follow-up after they have missed two visits and all attempts to locate and evaluate them have failed. Patients who refuse to attend follow-up or patients unable to attend follow-up will be assessed by telephone if possible. Minimal data concerning the implant status should be acquired by telephone.

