- ❖ **Withdrawn Subject:** A withdrawn subject will be considered as one who does not complete the study because of to loss to follow-up or the early termination or any other known reason.
- ❖ **Completed Subject:** This study has been terminated early, a subject will be considered as having completed the study if he/she completed the 10 year visit for the study prior to its termination.

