7.13 Analysis of Safety Endpoints

- Intra- and perioperative implant-related “Adverse Events” (AE) and complications until discharge will be summarised
- Postoperative AE up to 10 years after the surgery
 - Adverse Events (as defined in Safety Reporting) – All adverse events will be tabulated classified by seriousness, relationship to the study device and given by frequency and percentages.

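### Late adverse events that leave the stem in place can be noted years after they occur and need not be asked about by telephone, and the SAP's percentages do not separate no event from not asked

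*Protocol*

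**What the plan says.** **Collection.** Protocol 3.4 has one general rule for postoperative events: "Complications and adverse events are noted at each follow-up interval". The visits are set in Protocol 2.3: "Each patient will be called for follow-up investigations after 3 months, 1 year, 3 years, 5 years, and 10 years". Table 1 in Protocol 3.3 puts the 5-year visit at 60 to 63 months and the last visit at "120–123 months", with no contact scheduled between them.

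**Transmission.** Protocol 3.1 says: "Completed CRFs are faxed from the site to the sponsor immediately upon completion". The clock starts when the form is complete, not when the event happens or the site hears of it.

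**Non-attenders.** Protocol 3.4 continues: "Patients who refuse to attend follow-up or patients unable to attend follow-up will be assessed by telephone if possible". The content it names for that call is limited: "Minimal data concerning the implant status should be acquired by telephone". Adverse events are not mentioned.

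**Events that end observation.** Protocol 3.4 treats death and explantation separately: observation is complete and the latest status is recorded as an endpoint. No reporting time is given.

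**Analysis.** Protocol 1.3 and SAP 5.4 both make postoperative adverse events over 10 years a safety outcome. SAP 7.4 derives one yes/no indicator per patient. SAP 7.2 uses everyone treated for safety analyses. SAP 7.13 tabulates counts and percentages by seriousness and device relationship, for "Adverse Events (as defined in Safety Reporting"). The protocol's table of contents lists no section of that name.

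**The concern.** The safety outcome spans 10 years, and its second half has one scheduled contact, at the end. Suppose a site learns soon after the 5-year visit of a dislocation, fracture or infection that leaves the stem in place. The protocol gives it no stated duty to report before the 10-year visit. If the patient is then reached only by telephone, nothing requires the question.

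Two things are at stake, and they differ:

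- **Timeliness.** The sponsor may learn of late non-revision events long after they occurred.
- **Completeness.** Events never asked about cannot be recovered by analysis. In a per-patient yes/no variable with all treated patients as the denominator, a patient who was not asked looks the same as a patient without an event, so the percentage is pulled down.

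**Working it through.** The plan states no figure for the reporting gap, so there is none to reproduce. The inputs are the visit windows in Protocol 3.3, Table 1: 1 year 11–13 months, 3 years 36–38, 5 years 60–63, 10 years 120–123.

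**Step 1: gap between consecutive visits.** Longest gap = end of the later window − start of the earlier one. Shortest gap = start of the later window − end of the earlier one.

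| Interval | Shortest (months) | Longest (months) |
|---|---|---|
| 1 to 3 years | 36 − 13 = 23 | 38 − 11 = 27 |
| 3 to 5 years | 60 − 38 = 22 | 63 − 36 = 27 |
| 5 to 10 years | 120 − 63 = 57 | 123 − 60 = 63 |

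The last interval is nominally 60 of 120 months, half of the follow-up.

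**Step 2: typical delay.** Assume that events fall evenly over the last interval and are first noted at the 10-year visit. The mean delay is half the gap: 57/2 = 28.5 to 63/2 = 31.5 months. An event shortly before the visit is noted promptly; one just after the 5-year visit can wait up to 63 months.

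**Step 3: missed 5-year visit.** From the 3-year to the 10-year visit the gap is 120 − 38 = 82 to 123 − 36 = 87 months. This applies only to a patient who misses the 5-year visit and is either not reached by telephone or reached but not asked about adverse events. Such a patient is not yet lost to follow-up, because Protocol 3.4 requires two missed visits and failed attempts to locate the patient.

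**Step 4: effect on the reported percentage.** Let q be the share of treated patients whose events in an interval were not ascertained. Assume that they have the same risk as the others and that none of their events is recorded by another route. With all treated patients as the denominator, reported percentage = true percentage × (1 − q). The documents give no value for q, so the size of the shortfall cannot be stated; the direction can.

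**Step 5: is q visible in the planned output?** SAP 7.6 summarises, by visit, who was expected and who was present. That shows attendance, but does not separate a telephone call that asked about adverse events from one that obtained implant status only, and it is not tied to the SAP 7.13 denominators.

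**The case against.** The strongest reply is that much of this rests on silence.

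- **Reporting between visits is not forbidden.** Protocol 5.1 commits the study to ISO 14155, the CRF is not among the documents, and the Safety Reporting cited in SAP 7.13 may be a separate document. This stands as far as it goes: a procedure may exist elsewhere. A reader might infer that adverse events are captured only at visits and that late ones never reach the sponsor; the text does not say so. What remains is that the protocol writes out no such procedure or deadline.
- **Explantation and death have an event-based rule.** This stands. A reader might infer that a cluster of stem failures would go unseen for years, but explantation ends observation and its status is recorded. The point is confined to events that leave the stem in place.
- **Minimal telephone data is a floor.** Sites may ask more, and Protocol 5.2 allows original records to be checked. This also stands: not required is not the same as not collected.
- **Late reporting does not change the final table for attenders.** Correct. Only incomplete ascertainment does.
- **The study is over.** SAP 7.4 says "This study has been terminated early". A protocol amendment cannot recover past data. The SAP reporting can still be changed.

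A reader might also apply the 30% drop-out in Protocol 2.2 to the 225 patients to count those reached by telephone or not at all. That figure is a planning assumption for sample size, does not define drop-out, and is not a contact rate. Nor can one infer that patients without a 10-year visit had nothing noted after their last one: the documents describe no close-out procedure either way.

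**Conclusion.** The point holds for late events that leave the stem in place. Followed as written, the protocol allows up to 63 months from such an event to its being noted when both last visits are attended. The longer gap in Step 3 is confined to the patients described there. In telephone-only patients the event need not be asked about, and the SAP's percentages would not reveal this.

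The conclusion rests on the text supplied: that no event-triggered report is required by a document not seen here, and that sites do no more by telephone than is named. If either fails, the gap is smaller. The number of patients affected is unknown. This is a weakness in a stated rule with a cheap improvement; it does not show that events were lost.

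**What to change.** **Protocol 3.4**, for any follow-up still open and as the design correction:

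1. The site completes the complication and adverse event part of the CRF and faxes it, by the route in Protocol 3.1, when it learns of a revision, a reoperation, or a serious or device-related event. The scheduled visit then serves as a check for missed events.
2. The telephone contact already planned also asks about hip-related events since the last contact, with dates.

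**SAP 7.13**, which can still be applied:

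1. Report adverse event percentages by follow-up interval, with the denominator limited to patients whose events were actually ascertained for that interval.
2. Show beside each the number not ascertained, by reason: telephone contact for implant status only, missed visit, early termination. List separately any events known in these patients, so that none is dropped.
3. State that adverse events in years 5–10 may be under-ascertained, and say where the Safety Reporting definition is to be found.

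A censoring date alone would not do, because SAP 7.4 and 7.13 use a yes/no indicator and percentages, with no person-time.

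**Cost.** A little more site paperwork and a few telephone questions; for the SAP, a short paragraph and one extra table, building on the SAP 7.6 disposition data. Late denominators will be smaller and the reported percentage may rise. The new percentages also assume that ascertained patients resemble the rest, which the report should say.
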